5.2.3 Study drug preparation of durvalumab and tremelimumab

Based on average body WT of 75 kg, a fixed dose of 1500 mg Q4W durvalumab (equivalent to 20 mg/kg Q4W) and 75 mg Q4W tremelimumab (equivalent to 1 mg/kg Q4W) is included in the current study. for patients > 30kg in weight.

In patients whose weight falls to 30kg or less dosing should be delayed (for up to a maximum of 2 treatment cycles) until their weight returns to 30kg or higher when dosing can be resumed at the next cycle. If the weight does not return to 30kg or higher after a maximum 2 cycle delay then dosing should be permanently discontinued. Patients whose weight is below 30kg should not be dosed as they would be exposed to endotoxin levels that exceed the USP specification limit).

Preparation of durvalumab doses for administration with an IV bag

The dose of durvalumab for administration must be prepared by the Investigator's or site's designated IP manager using aseptic technique. Total time from needle puncture of the durvalumab vial to the start of administration should not exceed:

- 24 hours at 2°C to 8°C (36°F to 46°F)
- 4 hours at room temperature

If in-use storage time exceeds these limits, a new dose must be prepared from new vials. Infusion solutions must be allowed to equilibrate to room temperature prior to commencement of administration.

No incompatibilities between durvalumab and polyvinylchloride or polyolefin IV bags have been observed. Dose of 1500mg durvalumab for patients >30 kg will be administered using an IV bag containing 0.9% (w/v) saline or 5% (w/v) dextrose, with a final durvalumab concentration ranging from 1 to 20 mg/mL, and delivered through an IV administration set with a 0.2- or 0.22- μ m in-line filter. Add 30.0 mL of durvalumab (ie, 1500 mg of durvalumab) to the IV bag. The IV bag size should be selected such that the final concentration is within 1 to 20 mg/mL. Mix the bag by gently inverting to ensure homogeneity of the dose in the bag.

Durvalumab will be administered at room temperature (approximately 25°C) by controlled infusion into a peripheral or central vein. Following preparation of durvalumab, the entire contents of the IV bag should be administered as an IV infusion over approximately 60 minutes (\pm 5 minutes), using a 0.2- or 0.22- μ m in-line filter. Less than 55 minutes is considered a deviation.

The IV line will be flushed with a volume of IV solution equal to the priming volume of the infusion set used after the contents of the IV bag are fully administered, or complete the infusion according to institutional policy to ensure the full dose is administered and document if the line was not flushed.

Standard infusion time is 1 hour. However, if there are interruptions during infusion, the total allowed time should not exceed 8 hours at room temperature. The table below summarizes time allowances and temperatures.

Durvalumab hold and infusion times

Maximum time from needle puncture to start of administration	4 hours at room temperature, 24 hours at 2°C to 8°C
Maximum time for IV bag infusion, including interruptions	8 hours at room temperature

In the event that either preparation time or infusion time exceeds the time limits outlined in the table, a new dose must be prepared from new vials. Durvalumab does not contain preservatives, and any unused portion must be discarded.

Preparation of tremelimumab doses for administration with an IV bag

The dose of tremelimumab for administration must be prepared by the Investigator's or site's designated IP manager using aseptic technique. Total time from needle puncture of the tremelimumab vial to the start of administration should not exceed:

- 24 hours at 2°C to 8°C (36°F to 46°F)
- 4 hours at room temperature

If storage time exceeds these limits, a new dose must be prepared from new vials. The infusion solutions in the prepared final IV bag should be equilibrated to room temperature prior to administration.

No incompatibilities between tremelimumab and polyvinylchloride or polyolefin IV bags have been observed. However, administration sets containing cellulose-based filters should not be used with tremelimumab. Doses of 75 mg tremelimumab for patients >30 kg will be administered using an IV bag containing 0.9% (w/v) saline or 5% (w/v) dextrose, with a final tremelimumab concentration ranging from 0.10 mg/mL to 10 mg/mL, and delivered through an IV administration set with a 0.2- μ m or 0.22 μ m in-line filter. Add 3.8 mL (ie, 75 mg of tremelimumab) to the IV bag. In the event that a 50mg tremelimumab dose is required, add 2.5 mL (ie, 50 mg of tremelimumab) to the IV bag. The IV bag size should be selected such that the final concentration is within 0.10 to 10 mg/mL. Mix the bag by gently inverting to ensure homogeneity of the dose in the bag.

Tremelimumab will be administered at room temperature (approximately 25°C) by controlled infusion into a peripheral or central vein. Following preparation of tremelimumab, the entire contents of the IV bag should be administered as an IV infusion over approximately 60 minutes (\pm 5 minutes), using a 0.2- or 0.22- μ m in-line filter. Less than 55 minutes is considered a deviation.

The IV line will be flushed with a volume IV solution equal to the priming volume of the infusion set used after the contents of the IV bag are fully administered, or complete the infusion according to institutional policy to ensure the full dose is administered and document if the line was not flushed.

Standard infusion time is 1 hour. However, if there are interruptions during infusion, the total allowed time should not exceed 8 hours at room temperature. The table below summarizes time allowances and temperatures.

Tremelimumab hold and infusion times

Maximum time from needle puncture to start of administration	4 hours at room temperature, 24 hours at 2°C to 8°C
Maximum time for IV bag infusion, including interruptions	8 hours at room temperature

In the event that either preparation time or infusion time exceeds the time limits outlined in the table, a new dose must be prepared from new vials. Tremelimumab does not contain preservatives, and any unused portion must be discarded.

5.2.4 Monitoring of dose administration

Patients will be monitored during and after the infusion with assessment of vital signs at the times specified in the Study Protocol.

In the event of a \leq Grade 2 infusion-related reaction, the infusion rate of study drug may be decreased by 50% or interrupted until resolution of the event and re-initiated at 50% of the initial rate until completion of the infusion. For patients with a \leq Grade 2 infusion-related reaction, subsequent infusions may be administered at 50% of the initial rate. Acetaminophen and/or an antihistamine (eg, diphenhydramine) or equivalent medications per institutional standard may be administered at the discretion of the investigator. If the infusion-related reaction is \geq Grade 3 or higher in severity, study drug will be discontinued.

As with any antibody, allergic reactions to dose administration are possible. Appropriate drugs and medical equipment to treat acute anaphylactic reactions must be immediately available, and study personnel must be trained to recognize and treat anaphylaxis. The study site must have immediate access to emergency resuscitation teams and equipment in addition to the ability to admit patients to an intensive care unit if necessary.

5.2.5 Accountability and dispensation

The investigator shall take responsibility for and shall take all steps to maintain appropriate records and ensure appropriate supply, storage, handling, distribution and usage of investigational products in accordance with the protocol and any applicable laws and regulations. Clinical supplies will be provided by AstraZeneca and affixed with a clinical label in accordance with regulatory requirements. Clinical supplies must be stored in a secure, limited-access location under the storage conditions specified on the label. Receipt and dispensing of trial medication must be recorded by an authorized person at the trial site. Clinical supplies may not be used for any purpose other than that stated in the protocol.

5.2.6 Disposition of unused investigational study drug

The site will account for all investigational study drug dispensed and also for appropriate destruction. Certificates of delivery and destruction must be signed.

5.3 Radiation therapy

All subjects will be immobilized in a custom designed device in the appropriate position to isolate the index lesion. Radiotherapy treatment planning CT scans (with contrast, unless contraindicated) will be required to define the gross target volume (GTV) Clinical target volume (CTV) and planning target volume (PTV). The use of IV contrast is left to the discretion of the treating physician PET-CT and/or MRI imaging are preferred although not required to delineate volumes as accurately as possible. The treatment planning CT scan should be acquired with the subject in the same position and immobilization device, as for the treatment. Treatment planning will be performed using a 3D CT based treatment planning system. All tissues to be irradiated must be included in the CT scan. Planning CT scan will be obtained with a uniform slice thickness of less than or equal to 3 mm throughout and encompass the region of interest with sufficient margin for treatment planning.

All lesions with potential for respiratory motion should be evaluated by appropriate means including 4D CT scan and/or implanted fiducial marker(s). Respiratory motion management including but not limited to abdominal compression, active-breathing control (ABC), respiratory gating and fiducial marker tracking, will be employed for qualifying patients per standard clinical practice.

Daily image guidance will be employed for target localization. This is most commonly performed with volumetric imaging (cone-beam CT).

5.3.1 Radiotherapy Targeting and Treatment

HIGRT and SBRT have now been formally defined and described in a published guideline from the American College of Radiology and American Society for Therapeutic Radiology and Oncology (Potters 2004). This protocol will respect that guideline. The term stereotactic, for the purposes of this protocol, implies the targeting, planning, and directing of therapy using beams of radiation along any trajectory in 3-D space toward a target of known 3-D coordinates. The coordinate system is defined by reliable “fiducial” markers. This differs from conventional radiation therapy, in which therapy is directed toward less-than-reliable skin marks or bony landmarks that are indirectly referenced to the tumor (surrogates). This protocol will require treatments to be conducted with the use of a fixed 3-D coordinate system defined by fiducials. The coordinate system defined by the fiducials should be directly related to the radiation-producing device in a reproducible and secure fashion. Capability should exist to define the position of targets within the patient according to this same 3-D coordinate system. As such, the patient is set up for each treatment with the intention of directing the radiation toward a target according to the known 3-D coordinates as determined in the process of treatment planning. The nature of the fiducials themselves may include radiopaque markers or rods placed at known locations in a frame or fixed structure adjacent to the patient as well as use of the tumor itself as a fiducial (For example acquiring tomographic views of the tumor simultaneously with the treatment with a cone beam CT scan (CBCT)). Metallic “seeds” placed within the tumor will be allowed to constitute a fiducial so long as the methods are validated and a plan is in place to identify seed migration (e.g., redundant seeds placed).

5.3.2. Target Contouring

Gross Tumor Volume (GTV) is defined as all known gross disease encompassing the selected index lesion. The GTV will consist of the index lesion as visualized on CT +/- PET/CT, and/or MRI. Image fusion is encouraged when using multiple modalities to define the GTV.

Clinical Target Volume (CTV) will be the same as GTV for most cases. In case of uncertainty, GTV may be expanded to CTV by 2-3mm per clinician discretion.

Internal Gross Tumor Volume (IGTV) is defined for mobile index lesions at the discretion of the treating physician. For mobile index lesions, a 4-D CT scan will be acquired in order to account for the motion of the lesion during treatment. The IGTV will be defined as the union of the visualized index lesion on all gated CT data sets.

Planning Target Volume (PTV) will be defined as per convention for photon beam radiotherapy. A 3-dimensional margin of 3-5mm will be created on the CTV or IGTV (if available) to allow for daily set-up variance. For Proton beam radiotherapy, an additional range uncertainty is added during planning.

Organ at risk volume (OAR) is contoured as visualized on the planning CT or MR scan.

Planning organ at risk volume (PRV) is the OAR expanded for setup uncertainty or organ motion. The physician will contour the OAR. The dosimetrist will create the PRV by expanding the OAR by 1-3 mm, depending on the situation.

Pertinent Organs at Risk (OARs) in the index region are contoured as applicable to the region being treated by HIGRT or SBRT:

Spinal cord, Brain stem, Brachial plexus (roots & trunks), Cauda equina, Sacral plexus

Optic pathways – optic nerves, optic chiasm, Retina, Cornea

Carotid artery (Internal & common),

Cochlea & vestibular apparatus

Parotid and Sub mandibular glands

Skin (3-5 mm of body outline)

Larynx (infrahyoid supraglottis to bottom of cricoid. Only include the endolarynx within the cartilaginous framework

Other uninvolved mucosal structures eg: oral cavity & pharynx

Facial Bones : Mandible, Maxilla, temporal bone that pertain to index region

Esophagus

Heart and Pericardium

Lungs

Ribs

Trachea and Large/Central Bronchi

Bronchii – smaller airways

Liver

Stomach, Duodenum, Small Bowel

5.3.3. Radiation Treatment planning, dose fractionation and organs at risk specification

Computer based planning & quality assurance (QA) will be performed using our standard institutional HIGRT and SBRT guidelines, to deliver HIGRT or SBRT to the index lesion(s), including static 3D coplanar and/or non-coplanar beam arrangements as well as dynamic conformal arcs. Corrections for tissue heterogeneity, and robustness analysis (for Proton therapy) will be made. Treatment planning may be performed with 3D-CRT, IMRT, VMAT or, Proton beam RT (Pencil beam RT or Uniform scanning).

3D coplanar or non-coplanar beam arrangements will be custom designed for each case to deliver highly conformal prescription dose distributions. Non-opposing, non-coplanar beams are preferable. Typically, $>/= 5-10$ beams of radiation will be used with roughly equal weighting. Generally, more beams are used for lesions that are in very close proximity to a critical OAR to produce appropriately protective concave dose distributions with a steep dose gradient between the target lesion and the OAR.

For arc rotation techniques, a minimum of 340 degrees (cumulative for all beams) should be utilized.

Proton beam planning is performed with 2-4 beams. In order to obtain acceptable coverage, field aperture size and shape should correspond nearly identically to the projection of the PTV along a beam's eye view (i.e., no additional "margin" for dose buildup at the edges of the blocks or MLC jaws beyond the PTV). The only exception should be when observing the minimum field dimension of 3.5 cm when treating small lesions (see above).

Radiotherapy prescription: The dose prescription will be as follows: 24 Gy given in 3 fractions to PTV (80-95% IDL) delivered at 8 Gy per fraction every other day. however, a dose reduction to 6 Gy per fraction will be permitted if 8 Gy is not achievable due to dose constraints.

Dose Uniformity: 95% of the planning target volume (PTV) should be covered by the prescription dose (PTV V95%RX = 100%) and 99% of the planning target volume (PTV) should receive a minimum of 90% of the prescription dose (PTV V99%RX > 90%). 99% of the CTV should receive a minimum of 98% of the prescribed dose (CTV V99%RX >98%); however, higher isodoses (hotspots) of $> 105\%$ of prescribed dose must be manipulated to occur within the target and not in adjacent normal tissue.

Dose rate: For the purpose of this study, dose rate utilized will be that which is commissioned by the manufacturer and the medical physics group for external beam radiotherapy delivery by

the treating institution. There will be no special dose rate modifications required for this study.

Critical Organ Doses: For de novo cases (no prior RT) all the following critical organ dose-volume limits will be respected.

The following PRV dose constraints may be used as guidelines: (adopted from Timmerman RD. An overview of hypofractionation. Seminars of Radiation Oncology 2008 Oct;18(4):215-222 and Lo SS et al. Serious Complications Associated with Stereotactic Ablative Radiotherapy and Strategies to Mitigate the Risk. Clinical Oncology 2013 Jun;25(6):378-387).

Spinal cord PRV max 20 Gy

Spinal cord max 18 Gy

Brain stem max 22.5 Gy, 18 Gy (< 0.5cc)

Optic chiasm max 15 Gy, 12 Gy (< 0.2cc) (for bilateral blindness risk)

Ipsilateral Optic nerve max 18 Gy, 15 Gy (< 0.2cc)

Contralateral optic nerve max 12 Gy, 10 Gy (< 0.5cc)

Carotid artery max 15 Gy, (V12 Gy to < 30% of carotid volume)

Brachial plexus max 24 Gy, 20 Gy (< 3cc)

Esophagus* max 24 Gy, 17 Gy (< 5cc)

Heart/Pericardium max 27 Gy, 24 Gy (< 15cc)

Trachea* max 24 Gy, 15 Gy (< 4cc)

Bronchus max 24 Gy, 15 Gy (< 1cc)

Ribs max 27 Gy, 24 Gy (< 5cc)

Skin max 27 Gy, 24 Gy (<10cc)

Lung (Right & Left) – V20 < 10%, 11.4 Gy (< 1000cc) 10.5 Gy (< 1500cc)

Great vessels, non-adjacent wall max 27 Gy, 24 Gy (< 10cc)

Liver – spare >700cc to <=17.1 Gy

Stomach – max 22.2 Gy, 16.5 Gy to < 10cc

Colon – max 27 Gy, 24 Gy (<20cc)

Renal cortex (right and left) 15 Gy (>65%), 14.4 Gy (200cc)

Rest of OARS = ALARA

* avoid circumferential radiation

For re-irradiation cases, the above constraints do not apply. The treating physician's discretion would be used in such cases based on the previous dose exposure to various OARs as determined from the prior treatment plan and clinical goals.

Planning Priorities and Dose specifications

Every attempt will be made to successfully satisfy all of the planning goals and OAR criteria without deviation. All critical organ dose-volume limits will be respected. As far as possible, all OAR constraints will be met while providing full coverage to the PTV. In some cases, it may not be possible to meet all planning goals. In such cases, OAR constraints and PTV coverage will be balanced per the discretion of the treating physician. Brain stem, optic nerves, optic chiasm, spinal cord, brachial plexus, cauda equine and sacral plexus dose constraints must be respected over PTV coverage. In cases of other OAR constraints, which are not well validated, PTV coverage and OAR constraints must be balanced per clinical practice at the discretion of the treating physician.

Image Guidance:

Image guided RT (IGRT) is required with physician review per institutional QA requirements before each treatment is delivered. Cone beam CT will be matched to target volume to be treated and bony anatomy or other defined fixed fiducials. If CBCT is unavailable, orthogonal pair KV imaging matched to stable bony anatomy closest to PTV is acceptable.

6. TREATMENT PLAN

The Trial Flow Chart – in Protocol Synopsis, summarizes the trial procedures to be performed at each visit. Individual trial procedures are described in detail below. It may be necessary to perform these procedures at unscheduled time points if deemed clinically necessary by the investigator.

Furthermore, additional evaluations/testing may be deemed necessary by the Sponsor and/or AstraZeneca for reasons related to subject safety. In some cases, such evaluation/testing may be potentially sensitive in nature (e.g., HIV, Hepatitis C, etc.), and thus local regulations may require that additional informed consent be obtained from the subject. In these cases, such evaluations/testing will be performed in accordance with those regulations

6.1 Subject enrollment

6.1.1 Procedures for enrollment

Informed Consent

The Investigator must obtain documented consent from each potential subject prior to participating in a clinical trial.

Consent must be documented by the subject's dated signature or by the subject's legally acceptable representative's dated signature on a consent form along with the dated signature of the person conducting the consent discussion.

A copy of the signed and dated consent form should be given to the subject before participation in the trial.

The initial informed consent form, any subsequent revised written informed consent form and any written information provided to the subject must receive the IRB/ERC's approval/favorable opinion in advance of use. The subject or his/her legally acceptable representative should be informed in a timely manner if new information becomes available that may be relevant to the

subject's willingness to continue participation in the trial. The communication of this information will be provided and documented via a revised consent form or addendum to the original consent form that captures the subject's dated signature or by the subject's legally acceptable representative's dated signature.

The informed consent will adhere to IRB/ERC requirements, applicable laws and regulations and Sponsor requirements.

Inclusion/Exclusion Criteria

All inclusion and exclusion criteria will be reviewed by the investigator or qualified designee to ensure that the subject qualifies for the trial.

Medical History

A medical history will be obtained by the investigator or qualified designee. Medical history will include all active conditions, and any condition diagnosed within the prior 10 years that are considered to be clinically significant by the Investigator. Details regarding the disease for which the subject has enrolled in this study will be recorded separately and not listed as medical history.

Prior and Concomitant Medications Review

The investigator or qualified designee will review prior medication use, including any protocol-specified washout requirement.

Disease Details and Treatments

Disease Details

The investigator or qualified designee will obtain prior and current details regarding disease status.

Prior Treatment Details

The investigator or qualified designee will review all prior cancer treatments including systemic treatments, radiation and surgeries.

Subsequent Anti-Cancer Therapy Status

The investigator or qualified designee will review all new anti-neoplastic therapy initiated after the last dose of trial treatment. If a subject initiates a new anti-cancer therapy within 30 days after the last dose of trial treatment, the 30 day Safety Follow-up visit must occur before the

first dose of the new therapy. Once new anti-cancer therapy has been initiated the subject will move into survival follow-up.

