Subjects may withdraw consent at any time for any reason or be dropped from the trial at the discretion of the investigator should any untoward effect occur. In addition, a subject may be withdrawn by the investigator or the Sponsor if enrollment into the trial is inappropriate, the trial plan is violated, or for administrative and/or other safety reasons.

Subjects who are permanently discontinued from receiving investigational product will be allowed for safety per Appendix 2 or 3, including the collection of any protocol-specified blood specimens, unless consent is withdrawn or the subject is lost to follow-up or enrolled in another clinical study. All subjects will be followed for survival. Subjects who decline to return to the site for evaluations will be offered follow-up by phone every 3 months as an alternative.

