8.3.3 Withdrawal of informed consent for donated biological samples

If a subject withdraws consent to the use of donated samples, the samples will be disposed of/destroyed, and the action documented. As collection of the biological samples is an integral part of the study, then the subject is withdrawn from further study participation.

The Principal Investigator:

- Ensures that biological samples from that subject, if stored at the study site, are immediately identified, disposed of/destroyed, and the action documented
- Ensures the laboratory(ies) holding the samples is/are informed about the withdrawn consent immediately and that samples are disposed/destroyed, the action documented and the signed document returned to the study site
- Ensures that the subject is informed about the sample disposal.

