9.1 Progression free and Overall survival

Data on disease progression by RECIST criteria, and patient death will be recorded and used to calculate PFS and OS. Patients who have discontinued study therapy due to disease progression, toxicity, or withdrawal of consent will continue to be followed to collect data for this endpoint.

Subjects who have disease control following completion of 12 months of treatment or subjects who are withdrawn from durvalumab + tremelimumab treatment for reasons other than confirmed PD will continue to have objective tumor assessments (see Appendix 3).

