10.3.1 Study recording period and follow-up for adverse events and serious adverse events

Adverse events and serious adverse events will be recorded from time of administration of the first dose of investigational drug, throughout the treatment period and including the follow-up period (90 days after the last dose of durvalumab + tremelimumab).

During the course of the study all AEs and SAEs should be proactively followed up for each subject. Every effort should be made to obtain a resolution for all events, even if the events continue after discontinuation/study completion.

If a subject discontinues from treatment for reasons other than disease progression, and therefore continues to have tumor assessments, drug or procedure-related SAEs must be captured until the patient is considered to have confirmed PD and will have no further tumor assessments.

The investigator is responsible for following all SAEs until resolution, until the subject returns to baseline status, or until the condition has stabilized with the expectation that it will remain chronic, even if this extends beyond study participation.

Follow-up of unresolved adverse events

Any AEs that are unresolved at the subject's last visit in the study are followed up by the investigator for as long as medically indicated, but without further recording in the CRF. After 90 days, only subjects with ongoing investigational product-related SAEs will continue to be followed for safety.

AstraZeneca/MedImmune retains the right to request additional information for any subject with ongoing AE(s)/SAE(s) at the end of the study, if judged necessary.

Post study events

After the subject has been permanently withdrawn from the study, there is no obligation for the investigator to actively report information on new AE or SAEs occurring in former study subjects after the 90-day safety follow-up period for patients treated with durvalumab + tremelimumab. However, if an investigator learns of any SAEs, including death, at any time after the subject has been permanently withdrawn from study, and he/she considers there is a reasonable possibility that the event is related to study treatment, the investigator should notify the study sponsor and AstraZeneca/MedImmune Drug Safety.

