10.3.2 Reporting of serious adverse events

All SAEs will be reported, whether or not considered causally related to the investigational product, or to the study procedure(s). The reporting period for SAEs is the period immediately following the time that written informed consent is obtained through 90 days after the last dose of durvalumab + tremelimumab or until the initiation of alternative anticancer therapy. The investigator and/or Sponsor are responsible for informing the Ethics Committee and/or the Regulatory Authority of the SAE as per local requirements.

NOTE TO AUTHOR: For trials conducted in the United States, the following must be included (similar language must be included, referencing the appropriate health authority and reporting mechanism, for studies conducted outside of the United States). Note that all serious or unexpected adverse events must be reported to AstraZeneca regardless of the country where the study is conducted:

The investigator and/or sponsor must inform the FDA, via a MedWatch/AdEERs form, of any serious or unexpected adverse events that occur in accordance with the reporting obligations of 21 CFR 312.32, and will concurrently forward all such reports to AstraZeneca. A copy of the MedWatch/AdEERs report must be faxed to AstraZeneca at the time the event is reported to the FDA. It is the responsibility of the sponsor to compile all necessary information and ensure that the FDA receives a report according to the FDA reporting requirement timelines and to ensure that these reports are also submitted to AstraZeneca at the same time.

* A **cover page** should accompany the **MedWatch/AdEERs** form indicating the following:

- “Notification from an Investigator Sponsored Study”

- The investigator IND number assigned by the FDA
- The investigator's name and address
 - The trial name/title and AstraZeneca ISS reference number (ESR-16-11857)

* Sponsor must also indicate, either in the SAE report or the cover page, the ***causality*** of events ***in relation to all study medications*** and if the SAE is ***related to disease progression***, as determined by the principal investigator.

**** Send SAE report and accompanying cover page by way of email to AstraZeneca's designated mailbox:*** [contact]

If a non-serious AE becomes serious, this and other relevant follow-up information must also be provided to AstraZeneca and the FDA.

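### Sections 4.3, 6.1.1, 8.3.3 and 10.3.2 end follow-up earlier than Sections 8.1.3, 9.1, 10.3.1 and Appendices 2 and 3 require, so late adverse events may go uncollected for the primary safety endpoint

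*Combined protocol and SAP*

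**What the plan says.** **Passages that require longer follow-up**

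- Section 10.3.1 records AEs and SAEs from the first dose, "throughout the treatment period and including the follow-up period (90 days after the last dose of durvalumab + tremelimumab". For patients who stop for a reason other than progression, it adds that "drug or procedure-related SAEs must be captured until the patient is considered to have confirmed PD and will have no further tumor assessments".
- Appendices 2 and 3 schedule AE/SAE checks at Day 30, Month 2 and Month 3. Appendix 2 also logs subsequent anticancer therapy and continues scans every 8-12 weeks until confirmed progression, so it does not treat a new therapy as an exit.
- Section 9.1 says that patients who stop therapy "due to disease progression, toxicity, or withdrawal of consent will continue to be followed to collect data for this endpoint", meaning PFS and OS. It keeps tumour assessments going in those who stop without confirmed progression.
- Sections 4.3 and 8.1.3 follow all subjects for survival.

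**Passages that end follow-up earlier**

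- Section 6.1.1, under subsequent anticancer therapy: "Once new anti-cancer therapy has been initiated the subject will move into survival follow-up". If the new therapy starts within 30 days of the last dose, "the 30 day Safety Follow-up visit must occur before the" first dose of that therapy.
- Section 10.3.2 closes the SAE reporting period at 90 days "or until the initiation of alternative anticancer therapy".
- Section 4.3 provides the Appendix 2 or 3 safety follow-up "unless consent is withdrawn or the subject is lost to follow-up or enrolled in another clinical study".
- Section 8.3.3, on withdrawal of consent for donated samples: "As collection of the biological samples is an integral part of the study, then the subject is withdrawn from further study participation". Under Section 2.1.3 these samples serve an exploratory objective.

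**The concern.** Safety and tolerability is the primary endpoint, assessed in every enrolled patient (Sections 11.1 and 11.2.1). Section 11.3 relies on the upper confidence bound of the toxicity rate to exclude a clinically important increase from adding radiation. An event that is never collected moves that bound in the reassuring direction.

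The loss would not fall at random. It falls on patients who leave treatment early and go on to something else, including those who stopped because of toxicity. Two patients with the same event on Day 60 could be handled differently, depending on which section the staff applied. Events missed at the time are hard to recover later.

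The tumour endpoints are exposed less. A patient who stops without RECIST progression and then switches is scanned until confirmed progression under Appendix 2, but moves to survival follow-up under Section 6.1.1.

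**Working it through.** **1. The passages side by side**

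| Situation | Longer rule | Shorter rule |
|---|---|---|
| AE on Day 60, new therapy since Day 30 | Recorded (10.3.1; Appendices 2 and 3) | Patient is in survival follow-up (6.1.1) |
| SAE on Day 60, same patient | Recorded (10.3.1) | Outside the reporting period (10.3.2) |
| AE on Day 60, patient now in another study | Recorded (10.3.1) | Appendix follow-up has ended (4.3) |
| Stopped for toxicity without progression, then switched | Scans to confirmed progression (9.1; Appendix 2) | Survival follow-up (6.1.1) |
| Sample consent withdrawn | Followed for survival (4.3; 8.1.3) | Withdrawn from the study (8.3.3) |

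No section says which rule prevails.

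**2. Part of the window at risk**

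For a switch on day s after the last dose, the uncovered part of the 90-day window is (90 − s)/90. At s = 30 this is 60/90 = 67%.

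The stopping rule in Section 3.3 counts Grade 4 or higher drug-related events up to 30 days after the last infusion. A switch at s < 30 can remove 30 − s of those days. For example, at s = 14 it removes 16 of 30 days (53%), because the safety visit is brought forward and survival follow-up then begins.

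**3. The plan's own figures**

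Section 11.3 states precision within 22% and at least an 87% chance of seeing a toxicity of 10% prevalence.

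- Half-width: 1.96 × √(0.25/20) = 0.219.
- Detection: 1 − 0.9^20 = 0.878.

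Both reproduce, and both assume that all 20 patients are fully observed. With 19 the detection figure is 1 − 0.9^19 = 0.865, just below the stated 87%.

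**4. Illustration only**

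The documents give no early-exit rate. Assume that k of 20 patients exit early and that a share f of each one's risk for a 10% toxicity falls after exit. Detection is then 1 − 0.9^(20−k) × (1 − 0.1(1 − f))^k.

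| k | f = 0.25 | f = 0.5 | f = 1 |
|---|---|---|---|
| 2 | 87.2% | 86.5% | 85.0% |
| 4 | 86.4% | 84.9% | 81.5% |
| 6 | 85.7% | 83.2% | 77.1% |
| 10 | 84.0% | 79.1% | 65.1% |

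The column f = 1 is the extreme in which the toxicity appears only after exit. The table treats leaving early as unrelated to toxicity risk, which may not hold. It shows sensitivity to the two assumptions and does not estimate the loss in this trial.

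**The case against.** Section 6.1.1 never says that AE recording stops, and survival follow-up is not defined. The only schedules that collect survival status are Appendices 2 and 3, and both contain AE checks to Month 3. Section 10.3.2 governs reporting, so an earlier end there need not end recording under Section 10.3.1. Section 10.3.2.1 still covers deaths within 90 days of the last dose, and Section 10.3.1 asks for notification of later SAEs that the investigator learns of and thinks possibly related. The DLT window runs from the first dose (28 days in Section 6.4, 8 weeks in the synopsis), so these exits reach it only in a run-in patient who stops after the first or second dose. Events after a switch may be caused by the next therapy, so pooling them could overstate toxicity. Section 8.3.3 also gives a reason for its rule.

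Much of this stands, and it limits the size of the problem. It does not remove the conflict. Calling Section 6.1.1 ambiguous concedes that staff cannot tell what to collect. Section 4.3 is explicit about entry to another study, and Section 10.3.2 is explicit about SAE reporting. The late-SAE clause is passive and does not cover non-serious events. Confounding by the next therapy is a reason to tabulate those events separately, not to leave them uncollected.

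A reader might infer three stronger points that the documents do not support:

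- **PFS is censored at clinical deterioration and so biased upward.** Section 11.2.2 gives no censoring rule. The deterioration clause in Section 9 qualifies the need to confirm an initial assessment of progression, so most such patients would already have a progression assessment. A patient who switches because of recorded progression already has the PFS event.
- **Each patient withdrawn under Section 8.3.3 costs 1/20 of the primary data.** Section 11.1 keeps every enrolled patient in the analysis, so only information after the withdrawal is lost.
- **Different sites could apply different rules.** There is one centre. The inconsistency would be between patients or between staff.

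**Conclusion.** The conflict is real and concerns data collection for the primary endpoint. If the exit rules are followed, AEs between the switch and Day 90 may go uncollected, and a switch before Day 30 can also shorten the stopping-rule window. The toxicity rate and its upper bound may then be understated. Missed progression is a smaller matter, confined to patients who stop without RECIST progression and then start another therapy. On its wording, Section 8.3.3 ends all follow-up for a reason tied to an exploratory objective, against the commitment to follow every subject for survival.

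The 67% is arithmetic for a switch at Day 30. No shift in the toxicity rate in percentage points can be supported, because the documents give neither the share of patients who switch nor the rate of late events. The conclusion assumes that staff would apply the shorter rules at least some of the time. The passive notification of later related SAEs and the reporting of deaths within 90 days reduce the loss but do not close it.

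**What to change.** 1. Make Section 10.3.1 the governing rule and align Sections 4.3, 6.1.1 and 10.3.2 to it: AEs and SAEs are collected to 90 days after the last study dose, regardless of new anticancer therapy or entry to another study, unless the patient withdraws consent to follow-up.
2. Record the start date of any new therapy and tabulate events after it separately. Add the subsequent-therapy row of Appendix 2 to Appendix 3.
3. For patients who stop without progression, state that available scan results are collected until progression or death, including after a switch.
4. Change Section 8.3.3 so that withdrawing sample consent ends sample use only. AE, scan and survival data collection continues unless the patient also withdraws from follow-up. Reconcile Section 8.3.3 with Section 4.3 on what happens to study treatment in that case.
5. Correct Section 9.1, which sends patients without confirmed progression to Appendix 3. Their schedule is in Appendix 2.

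The cost is wording changes, a few more telephone or record-based contacts, and some events confounded by the next therapy, which the separate tabulation handles. The sample size does not change.
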